**Data Analysis:**

The core population (CP) is defined as all patients of the target population (TP) (definition see above), who have started the treatment combination recommended in the current local label for their disease characteristics. Patients not receiving the treatment recommended in the local label will be summarized in the non-core population (NCP). In addition, the core population with sufficient follow-up data (CPSFU) is defined as all CP patients, who have (i) evaluable HCV RNA data ≥70 days after the last actual dose of the ABBVIE REGIMEN or (ii) a HCV RNA value ≥50 IU/mL at the last measurement or (iii) had HCV RNA < 50 IU/mL at the last measurement, but no HCV RNA measurement ≥70 days after the last actual dose of the ABBVIE REGIMEN due to reasons related to safety (e.g. dropped out due to adverse event) or incomplete efficacy information (e.g. virologic failure such as relapse is reported in the electronic case report form (eCRF) but date and value of the corresponding HCV RNA test is missing). The safety population (SP) is defined as all patients who received at least one dose of the ABBVIE REGIMEN.

Descriptive and exploratory statistical methods will be used to analyze the data of the study. All baseline and disease characteristics will be summarized for the CP stratified by the CP analysis groups (based on genotype 1 subtype, fibrosis status, treatment experienced or naïve), which are relevant for scheduled treatment combination (± Dasabuvir, ± RBV) and duration (12 or 24 weeks). In addition, baseline summaries will be repeated for the SP and TP without stratification into subgroups. Further details of analysis populations and the CP analysis groups will be specified in the statistical analysis plan (SAP).

The primary effectiveness analysis will be performed for CP patients, stratified by the CP analysis groups. Response rates (i.e. SVR12 rate, end of treatment [EoT] response rate, relapse rate, viral breakthrough) will be determined for the various CP analysis groups. The

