## 9.7 Data Analysis

### 9.7.1 Analysis Population, Time Windows and Handling of Missing Data

The target population (TP) is defined as all patients who fulfill the criteria specified in Section 9.2.1. The core population (CP) is defined as all patients of the TP, who have started the treatment combination recommended in the current local label for their disease characteristics. Patients not receiving the treatment recommended in the local label will be summarized in the non-core population (NCP). In addition, the core population with sufficient follow-up data (CPSFU) is defined as all CP patients, who fulfil one of the following criteria:

- (1) evaluable HCV RNA data  $\geq 70$  days after the last actual dose of the ABBVIE REGIMEN (i.e. data within the SVR12 time window)
- (2) a HCV RNA value  $\geq 50$  IU/mL at the last measurement post-baseline (i.e. no virological response achieved at the last measurement on-treatment or post-treatment)
- (3) HCV RNA  $< 50$  IU/mL at the last measurement post-baseline, but no HCV RNA measurement  $\geq 70$  days after the last actual dose of the ABBVIE REGIMEN due to reasons related to safety (e.g. dropped out due to AE) or incomplete efficacy information (e.g. virologic failure such as relapse is reported in the eCRF but date and value of the corresponding HCV RNA test is missing). This means only patients who had virological response at their last on-treatment or post-treatment measurement, but had no HCV RNA measurements  $\geq 70$  days post-treatment for reasons not related to safety or effectiveness (e.g. lost-to-follow-up or patient not willing to perform an additional HCV RNA test  $\geq 70$  days post-treatment) will be excluded from this analysis.

The Safety Population (SP) is defined as all patients who received at least one dose of the ABBVIE REGIMEN.

In accordance with the non-interventional nature of the study all HCV RNA measurements will be performed at the sole discretion of the physician and all HCV RNA measurements have to be entered into the eCRF. All recorded HCV RNA values will be assigned to appropriate time points (baseline, on-treatment visits, EoT visit, post-treatment visits). The time windows for the assignments will be specified in the statistical analysis plan (SAP).

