**Safety population [SP]**

The safety population is defined as all enrolled patients who received at least one dose of the ABBVIE REGIMEN. The prescribed ABBVIE REGIMEN needs to be known.

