### SP analysis groups

The SP analysis groups are defined according to the treatment regimen and patient's fibrosis status. The standard summaries by SP groups in the safety population are as follows (if not specified otherwise):

- Total (regardless of cirrhosis status)
  - (1) Total
  - (2) 2DAA w/o RBV
  - (3) 2DAA + RBV
  - (4) 3DAA w/o RBV
  - (5) 3DAA + RBV
- Patients with cirrhosis
  - (6) Total
  - (7) 2DAA w/o RBV
  - (8) 2DAA + RBV
  - (9) 3DAA w/o RBV
  - (10) 3DAA + RBV
- Patients without cirrhosis
  - (11) Total
  - (12) 2DAA w/o RBV
  - (13) 2DAA + RBV
  - (14) 3DAA w/o RBV
  - (15) 3DAA + RBV
- Patients with unknown fibrosis status
  - (16) Total
  - (17) 2DAA w/o RBV
  - (18) 2DAA + RBV
  - (19) 3DAA w/o RBV
  - (20) 3DAA + RBV

(2DAA - paritaprevir/r-ombitasvir, 3 DAA - paritaprevir/r-ombitasvir + dasabuvir, RBV – ribavirin taken, w/o RBV – no ribavirin taken)

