#### 4.2.8 Analyses of Safety

All safety variables will be summarized for patients in the SP using descriptive statistical methods stratified by treatment regimen and cirrhosis status and overall.

An overview of tables for the individual values is given in Table 13.

The layouts of the tables mentioned above are provided in Part II of the SAP (Table Shells).

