#### **4.2.8.3 Adverse Events**

All tolerability variables will be summarized using descriptive statistical methods for the SP stratified by treatment regimen and cirrhosis status and overall.

AEs will be coded using MedDRA. A glossary will show the verbatim terms and the corresponding coded terms used (see Table 13).

The number and percentage of patients with treatment-emergent AEs (i.e. any reported event that begins or worsens in severity after initiation of study drug through 30 days post-study drug dosing including those who are related to the study drug independent of the occurrence and those where the date of onset is missing) will be tabulated by primary MedDRA SOC and PT.

Corresponding summary tables will be provided for all serious treatment-emergent AEs and additional for all non-serious treatment-emergent AEs. In the table of non-serious AEs (that must exclude any SAE) only preferred terms that occurred at a frequency of  $\geq 5\%$  in any treatment group will be displayed (no SOCs will be displayed).

The tabulation of the number of patients with treatment-emergent AEs by severity (AEs by severity [mild, moderate, severe], AEs leading to death, AEs leading to hospitalization) and relationship to study drug will also be provided (ABBVIE regimen, ribavirin, medication error -

paritaprevir/r-ombitasvir, medication error – dasabuvir, ABBVIE regimen withdrawn, ribavirin withdrawn).

Patients reporting more than one AE for a given MedDRA PT will be counted only once for that term using the most severe incident for the severity summary table and the most related for the relationship summary table. Patients reporting more than one type of event within a SOC will be counted only once for that SOC.

The frequency of pregnancies will be displayed as well.

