**Table 12 Overview of Outputs for Safety Variables**

Output Title	Output Short Name	Analysis Population
Exposure to Study Medication by Treatment Regimen and Cirrhosis Status - SP - <country>	tesm_<c>_tc_sp	Safety population
Unintended Medication Error/ Pregnancy by Treatment Regimen and Cirrhosis Status -- SP - <country>	tum_<c>_tc_sp	Safety population
Treatment-emergent AEs by Treatment Regimen and Cirrhosis Status - SP - <country>	tae_<c>_tc_sp	Safety population
Serious Treatment-emergent AEs by Treatment Regimen and Cirrhosis Status - SP - <country>	tsae_<c>_tc_sp	Safety population
Non-Serious Treatment-emergent AEs by Treatment Regimen and Cirrhosis Status - SP - <country>	tnsae_<c>_tc_sp	Safety population
Treatment-emergent AEs by Severity by Treatment Regimen and Cirrhosis Status - SP - <country>	taes_<c>_tc_sp	Safety population
Treatment-emergent AEs Leading to Death by Treatment Regimen and Cirrhosis Status - SP - <country>	taed_<c>_tc_sp	Safety population
Treatment-emergent AEs Leading to Hospitalization by Treatment Regimen and Cirrhosis Status - SP - <country>	taeh_<c>_tc_sp	Safety population
Treatment-emergent AEs Possibly Related to ABBVIE Regimen by Treatment Regimen and Cirrhosis Status - SP - <country>	taera_<c>_tc_sp	Safety population
Treatment-emergent AEs Possibly Related to Ribavirin in Patients taking RBV by Treatment Regimen and Cirrhosis Status - SP - <country>	taerr_<c>_tc_sp_RB V	Safety population: patients taking RBV
Treatment-emergent AEs Caused by Medication Error - Paritaprevir/r-Ombitasvir - by Treatment Regimen and Cirrhosis Status - SP - <country>	taempo_<c>_tc_sp	Safety population
Treatment-emergent AEs Caused by Medication Error - Dasabuvir - in Patients taking 3DAA by Treatment Regimen and Cirrhosis Status - SP - <country>	taemd_<c>_tc_sp_3d aa	Safety population: patients taking 3DAA
Treatment-emergent AEs Leading to Withdrawal of ABBVIE Regimen by Treatment Regimen and Cirrhosis Status - SP - <country>	taewa_<c>_tc_sp	Safety population
Treatment-emergent AEs Leading to Withdrawal of Ribavirin in Patients taking RBV by Treatment Regimen and Cirrhosis Status - SP - <country>	taewr_<c>_tc_sp_RB V	Safety population: patients taking RBV
Listing of SAEs - SP - <country>	lsae_<c>_sp	Safety population
Glossary for AEs - <country>	tgae_<c>	-
Co-medication by Treatment Regimen and Cirrhosis Status - SP - <country>	tcom_<c>_tc_sp	Safety population

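### The SAP narrows the protocol's safety population to patients whose prescribed regimen is known, without declaring it, so a dosed patient with an undocumented regimen would be in no planned safety output

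*SAP*

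**What the plan says.** The protocol defines the safety population twice, in the abstract ("The safety population (SP) is defined as all patients who received at least one dose of the ABBVIE REGIMEN") and in section 9.7.1 ("The Safety Population (SP) is defined as all patients who received at least one dose of the ABBVIE REGIMEN"). Neither place adds a further condition. Section 9.7.6 stratifies tolerability by combination treatment and scheduled duration, but does not make membership of the population depend on knowing them.

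SAP section 4.2.1 starts in the same way: "The safety population is defined as all enrolled patients who received at least one dose of the ABBVIE REGIMEN". It then adds: "The prescribed ABBVIE REGIMEN needs to be known". The same sentence stands in the SAP's definition of the target population (TP).

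The SAP ties the safety analysis to this population. Section 4.2.8 states: "All safety variables will be summarized for patients in the SP using descriptive statistical methods stratified by treatment regimen and cirrhosis status and overall". Section 4.2.8.3 repeats this for adverse events: "All tolerability variables will be summarized using descriptive statistical methods for the SP stratified by treatment regimen and cirrhosis status and overall". Section 4.2.8.4 does the same for laboratory data. The SAE listing in Table 12 is entitled "Listing of SAEs - SP - <country>".

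The SP analysis groups in section 4.2.1 contain a Total in each fibrosis block, four regimen groups per block, and a block headed "Patients with unknown fibrosis status". There is no group for an unknown regimen.

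**The concern.** A safety population is normally defined by exposure alone, so that each exposed patient's events count whatever the quality of the record. Under the SAP, membership also depends on whether one item was documented. A patient known to have taken the drug can be removed because the form does not say which combination was prescribed.

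Two things are at stake. The first is agreement between the documents: the SAP changes a population that the protocol defines, and a reader who relies on the protocol would think that all dosed patients are in the safety tables. The second is completeness of the statistical safety record. Protocol section 9.7.6 wants serious and non-serious events and pregnancies reported for patients included in the study. SAEs and deaths in a study of this size may be few, so omitting even one patient could matter.

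**Working it through.** No figure in the plan depends on this definition, so there is none to reproduce. The check compares the definitions and traces the population of each safety output.

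**1. Definitions.**

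| Source | Dose criterion | Further condition |
|---|---|---|
| Protocol abstract, Data Analysis | at least one dose | none |
| Protocol 9.7.1 | at least one dose | none |
| SAP 4.2.1, Safety population | enrolled, at least one dose | prescribed regimen known |

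A dosed patient with an undocumented regimen is inside the first two and outside the third.

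**2. Is the change declared?** The SAP does flag other departures. Section 4.1.1 says that the upper limit of the SVR12 window is new, and section 4.2.8.4 says that the protocol's shift tables are replaced. It gives no flag or reason for this condition.

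**3. Is there another output that would catch these patients?** In Table 12, every output on adverse events, SAEs, deaths, hospitalisation, withdrawal, medication error or pregnancy, and laboratory values has the SP or a subset of it as its population. So does the SAE listing. Only the two coding glossaries carry no population. No adverse-event output uses the enrolled population. Because the TP has the same condition, these patients are also outside the core population (CP) and the non-core population, which are both subsets of the TP. Reasons for ending the study, death among them, are tabulated for the SP and CP only (SAP 4.2.5).

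**4. How does the SAP treat similar gaps?** Unknown fibrosis status has its own SP block. Unknown genotype has a row in the enrolled-population groups. Co-medication without a profile has its own category (4.2.8.2). Events with a missing onset date count as treatment-emergent (4.2.8.3). In each case the record is kept. The Total groups do not need the regimen, so a missing regimen does not prevent a patient from being counted overall.

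**5. Possible size (illustration only).** Assume that all 650 planned patients are dosed, that k of them have an unknown regimen, and that each has SAE risk r independently. None of these values for k or r comes from the documents. The chance that at least one excluded patient had an SAE is 1 − (1 − r)^k.

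| k (share of 650) | SP size, 650 − k | r = 2% | r = 3% | r = 5% |
|---|---|---|---|---|
| 0 | 650 | 0% | 0% | 0% |
| 1 (0.2%) | 649 | 2% | 3% | 5% |
| 3 (0.5%) | 647 | 6% | 9% | 14% |
| 7 (1.1%) | 643 | 13% | 19% | 30% |
| 13 (2.0%) | 637 | 23% | 33% | 49% |
| 33 (5.1%) | 617 | 49% | 63% | 82% |

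For the effect on a rate, assume 20 patients with an SAE among 650 dosed: 20/650 = 3.08%. If 13 patients are excluded and none had an SAE, the SP rate is 20/637 = 3.14%. If 3 of the 13 had one, it is 17/637 = 2.67%. The rate moves by a fraction of a percentage point; the plainer consequence is that individual cases would be absent from the listing.

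**The case against.** The strongest reply is that the affected set may be empty. Prescription precedes the offer to participate, and eligibility requires receipt of the regimen in line with the label. Regimen initiation is a baseline item in the protocol's documentation schedule, and automated checks and queries are planned. A patient with a confirmed dose and a regimen that stays unknown would be an unusual data failure. This stands as a limit on weight. It does not show that the case cannot arise: only available routine data are collected, and neither document says that the regimen is a mandatory field.

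A second reply is that the protocol leaves further details of the analysis populations to the SAP, and that tables stratified by regimen need the regimen. But removing dosed patients alters the definition instead of detailing it, and the Total groups and the SAE listing do not need the regimen.

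Several stronger readings are tempting and are not supported:

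- **That the events are lost altogether.** SAP 4.2.5 and 4.2.10 provide for tabulating exclusions and their reasons, a disposition listing covers all enrolled patients, and the adverse-event glossary has no SP restriction. SAE reporting to the sponsor within 24 hours (protocol 11.5) is untouched. None of these replaces an adverse-event table or the SAE listing, but the exclusion would be visible.
- **That a known number of patients is affected.** The documents give no count, and any percentage is an assumption.
- **That they are excluded because they fit no regimen column.** This is a plausible guess; the SAP states no reason.
- **That exclusion selects early drop-outs.** The prescribed regimen is recorded at baseline, before on-treatment drop-out can occur. Poor charting remains a possible mechanism, but the documents do not show it.

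**Conclusion.** The point holds as a departure of the SAP from the protocol. The added condition narrows a population that the protocol defines by dose alone, the change is undeclared, and no planned safety output covers a dosed patient who fails it. This follows from the text and rests on no assumption.

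The practical size is unknown and may be nil. With no affected patients nothing changes in the results. With a handful, overall rates would barely move, but single SAEs or deaths could be missing from the study's tables and listing. The illustrative probabilities depend wholly on the assumed counts and risks. The correction is worth making because it is cheap and the sponsor can settle the size now: the SAP describes four interim analyses as already performed, each with patient disposition for the enrolled population, so the number excluded for an unknown regimen can be counted from data in hand.

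**What to change.** Delete the known-regimen sentence from the SP definition in SAP 4.2.1. Count dosed patients with an unknown regimen in the SP Total groups, (1) overall and (6), (11) or (16) according to fibrosis status, and include them in the SAE listing. If any exist, show an unknown-regimen group, as is done for unknown fibrosis status. The adverse-event glossary needs no change.

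If the sponsor prefers to keep the condition, the SAP should state that it departs from the protocol, give the reason, and add a listing of adverse events, SAEs and deaths for dosed patients outside the SP.

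In either case, declare the same condition in the TP definition as a departure, because the protocol's TP criteria do not contain it.

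The cost is a wording change and minor edits to the SP table shells: up to one extra group in each of the four fibrosis blocks, or none if no such patient exists. No new data are needed.

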### EP and TP analysis groups

The EP/TP analysis groups are defined according to the patient's fibrosis status and genotype/subtype and standard summaries are structured as follows:

- Total (regardless of cirrhosis status)
  - (1) Total (regardless of genotype)
  - (2) G1 (Total)
  - (3) G1a (including mixed G1 subtypes and patients with G1 unknown subtype)
  - (4) G1b
  - (5) G4 (non-G1)
  - (6) Other/unknown genotype (*only for EP*)
- Patients with cirrhosis
  - (7) Total (regardless of genotype)
  - (8) G1 (Total)
  - (9) G1a (including mixed G1 subtypes and patients with unknown G1 subtype)
  - (10) G1b
  - (11) G4 (non-G1)
  - (12) Other/unknown genotype (*only for EP*)
- Patients without cirrhosis
  - (13) Total (regardless of genotype)
  - (14) G1 (Total)
  - (15) G1a (including mixed G1 subtypes and patients with unknown G1 subtype)
  - (16) G1b
  - (17) G4 (non-G1)
  - (18) Other/unknown genotype (*only for EP*)
- Patients with unknown fibrosis status
  - (19) Total (regardless of genotype)
  - (20) G1 (Total)
  - (21) G1a (including mixed subtypes and patients with unknown subtype)
  - (22) G1b
  - (23) G4 (non-G1)
  - (24) Other/unknown genotype (*only for EP*)

(HCV genotypes will be combined as follows: G1 [total], G1a\*, G1b, G4 [non-G1]. \* includes mixed or other G1 subtypes and patients with unknown G1 subtypes.

Most recent stage of liver fibrosis will be categorized as follows: No cirrhosis/Transition to cirrhosis, Cirrhosis. Only one method should be selected by the physicians to report stage of fibrosis.

Nevertheless, if there are multiple answers the following priority will be used:

1. Biopsy,
2. Non-invasive,
3. Clinical/best guess.

For biopsy as assessment method the respective categories are defined as follows:

- “No cirrhosis” is defined by “No fibrosis”, “Mild/minimal fibrosis”, “Moderate fibrosis”
- “Transition to cirrhosis” is defined by “Advanced Fibrosis”
- “Cirrhosis” is defined by “Cirrhosis”.)

### **CP analysis groups and related treatment regimens**

The CP analysis groups are defined according to the patient's fibrosis status and genotype/subtype. The standard summaries by CP analysis groups in the CP and CPSFU population are structured follows (is not specified otherwise):

- Total (regardless of cirrhosis status)
  - (1) Total (regardless of genotype)
  - (2) G1 (Total)
  - (3) G1a (including mixed subtypes and patients with unknown subtype)
  - (4) G1b
  - (5) G4 (non-G1)
- Patients with cirrhosis
  - (6) Total (regardless of genotype)
  - (7) G1 (Total)
  - (8) G1a (including mixed subtypes and patients with unknown subtype)
  - (9) G1b
  - (10) G4 (non-G1)
- Patients without cirrhosis
  - (11) Total (regardless of genotype)
  - (12) G1 (Total)
  - (13) G1a (including mixed subtypes and patients with unknown subtype)
  - (14) G1b
  - (15) G4 (non-G1)

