**Confidential Information**

randomized to 12 or 24 weeks of therapy. Overall 92% and 96% of patients achieved SVR following treatment for 12 or 24 weeks, respectively. Analysis of subgroups demonstrated that the small difference in SVR between treatment arms was due largely to the subgroup of genotype 1a treatment-experienced prior null responders treated for 12 weeks who achieved an SVR of 80%. This subgroup of patients achieved an SVR of 93% when treated for 24 weeks. Among genotype 1a infected patients, partial responders and relapsers had higher SVR rates than null responders in the 12 week treatment group, while similar SVR rates were seen among the null responders, partial responders and relapsers treated for 24 weeks, suggesting that the longer duration of 24 weeks is required only for cirrhotic genotype 1a null responders. SVR rates were very high across all subgroups in genotype 1b treatment-experienced patients treated for 12 and 24 weeks.

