### 9.7.2 Demographics and Disease Characteristics

All baseline and disease characteristics will be summarized for the CP stratified by the CP analysis groups (i.e. based on genotype 1 subtype, fibrosis status, treatment experienced or naïve), which are relevant for scheduled treatment combination (ABBVIE REGIMEN  $\pm$  RBV) and duration (12 and 24 weeks). In addition, baseline summaries will be repeated for the SP and the TP without stratification into subgroups. Summary statistics (n, mean, median, standard deviation [SD], and range) will be generated for continuous variables (e.g. age and body mass index [BMI]). The number and percentage of patients will be presented for categorical variables (e.g. gender and race). Further details of analysis populations and the CP analysis groups will be specified in the SAP, taking into account the ABBVIE REGIMEN recommended in the current local label for various patient groups.

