### 9.7.3 Effectiveness Analysis

The primary effectiveness analysis on clinical outcomes will be performed on all patients in the CP stratified by the CP analysis groups. Due to the non-interventional nature of this study several different methods for determination of the HCV RNA value can be applied. For the purpose of the statistical analysis, a HCV RNA measurement is considered  $\leq 50$  IU/mL,

- if a PCR test was used
- and the test result is undetectable and the LLoD of the test is  $\leq 50$  IU/mL or the test result is unquantifiable and the LLoQ is  $\leq 50$  IU/mL

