### 9.7.3.3 Statistical Methods for Analysis of Effectiveness Variables

The simple percentage of patients achieving SVR12 will be calculated and a two-sided 95% confidence interval (CI) of the percentage based on the Wilson's Score method will be computed.

Corresponding methods will be used for other response rates (EoT response rate, relapse rate, viral breakthrough). The relapse rates will be estimated in patients of the CP analysis groups with EoT response and sufficient HCV RNA measurements post-treatment. Viral breakthrough rates will be estimated in all patients of the CP analysis groups, who have at least one undetectable HCV RNA measurement on-treatment and at least one on-treatment or EoT measurement thereafter.

Univariate and multiple logistic regression (MLR) methods will be used to investigate the impact of the following explanatory covariates on SVR12:

- Key demographic information
- Mode of CHC infection
- HCV RNA level at baseline
- Most recent stage of liver fibrosis
- HCV genotype and subtype (if available)
- Type of treating institute
- Liver and/or CHC related co-morbidities
- Key clinical chemistry and hematology laboratory variables at baseline
- In treatment experienced patients only:
  - Most recent prior treatment for CHC
  - Outcome of most recent prior CHC treatment

Further details and additional covariates will be specified in the SAP.

These analyses will be of exploratory nature, data driven, and will be repeatedly performed for the CP. Backward selection procedures will be applied to generate the final MLR models which consider only covariates for which the percentage of patients with available data is greater than 80% of the patient group analyzed. A p-value <0.05 will be used for the covariates to stay in the model in a backward elimination step. Logistic

---

Confidential Information

regression methods will also be used to investigate the impact of treatment adherence on SVR12.

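### The SAP omits, without comment, the naive/experienced factor of the core-population groups and two prior-treatment covariates named in the protocol, so no listed output gives SVR12 with a CI by prior treatment

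*SAP*

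**What the plan says.** **Protocol.** The abstract (Data Analysis) describes the CP analysis groups as "based on genotype 1 subtype, fibrosis status, treatment experienced or naïve", and Section 9.7.2 repeats the same three factors. Section 9.7.3 then ties the main analysis to them: "The primary effectiveness analysis on clinical outcomes will be performed on all patients in the CP stratified by the CP analysis groups". Section 9.7.2 also passes work on: "Further details of analysis populations and the CP analysis groups will be specified in the SAP". In Section 9.7.3.3 the covariates for the SVR12 regression include, for experienced patients only, the latest earlier regimen and "Outcome of most recent prior CHC treatment". That section lets the SAP give further detail and add covariates.

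**SAP.** Section 4.2.1 states: "The CP analysis groups are defined according to the patient's fibrosis status and genotype/subtype". The same two factors govern the standard tables for both populations, as the text across the sentence break shows: "fibrosis status and genotype/subtype. The standard summaries by CP analysis groups in the CP and CPSFU population". It lists 15 groups: five genotype rows in each of three cirrhosis layers. Section 4.2.7.1 runs the primary analysis by genotype, by cirrhosis status and overall. The covariate list in Section 4.2.7.2.1 has a naive/experienced term but neither covariate specific to experienced patients. Outside the regression, prior treatment appears in the baseline tables (4.2.6.2, 4.2.6.3) and in the regimen-by-pretreatment tables (4.2.5). None of these shows SVR12.

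**The concern.** A factor that the protocol names for stratifying the primary endpoint is missing from the SAP, and the SAP does not say so. It does announce other departures: the upper limit on the SVR12 window (Section 4.1.1) and the replacement of the laboratory shift tables (Section 4.2.8.4). A reader of the final report would find no SVR12 rate by prior treatment and could not tell whether this was a decision or an oversight.

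The covariates matter for a second reason. Predictors of response are the first secondary objective (Protocol 8.2.2). The protocol's own background singles out prior null response as the setting where SVR was lowest, and a naive/experienced flag cannot show that, because it pools null responders with partial responders and relapsers.

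**Working it through.** **1. The documents side by side.**

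| Item | Protocol | SAP |
|---|---|---|
| CP group factors | genotype 1 subtype, fibrosis, naive/experienced (abstract, 9.7.2) | genotype/subtype, fibrosis (4.2.1) |
| Strata of primary SVR12 analysis | the CP groups (9.7.3) | genotype, cirrhosis, overall (4.2.7.1) |
| Covariates in experienced patients | latest regimen; its result (9.7.3.3) | neither (4.2.7.2.1) |
| Output giving an SVR12 rate by prior treatment | implied by the strata | none in Table 8 |

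**2. The plan's precision figures.** These are in Protocol 9.5 and SAP 3.2. The Wilson interval has centre (p + z²/2n)/(1 + z²/n) and half-width z/(1 + z²/n) × √[p(1−p)/n + z²/4n²]. With p = 0.95 and z = 1.96:
- n = 620: 92.99 to 96.46, width 3.47 (plan: 3.5)
- n = 590: 92.93 to 96.49, width 3.55 (plan: 3.6)
- n = 62: 86.49 to 98.26, width 11.77 (plan: 11.8)

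All three are reproduced. The plan treats a width below 12 points as precise enough for subgroups.

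**3. Naive minus experienced.** Protocol Table 1 is the only place that sets the two against each other (non-cirrhotic, 12 weeks):
- G1a with ribavirin: 95–97 against 96, so −1 to +1 point
- G1b with ribavirin: 98–99.5 against 97, so +1 to +2.5 points
- G1b without ribavirin: 99 against 100, so −1 point

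With the largest gap (2.5 points) and an assumed experienced share of 20–50%, the pooled rate lies 0.2 × 2.5 = 0.5 to 0.5 × 2.5 = 1.25 points below the naive rate.

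**4. The 80% figure.** In Protocol 7.1 it belongs to "genotype 1a treatment-experienced prior null responders treated for 12 weeks who achieved an SVR of 80" (per cent), in a trial of cirrhotic patients. The whole 12-week arm reached 92%, so the gap is 92 − 80 = 12 points, between one subgroup and the arm that contains it. At 24 weeks the gap is 96 − 93 = 3 points. The protocol gives no naive rate and no all-experienced rate in cirrhotic patients.

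**5. Precision of the missing breakdown.** The documents give no experienced share; 20–50% is assumed, with SVR12 at 95%.

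| Set | Experienced: n, width | Naive: n, width |
|---|---|---|
| Whole CP, 620 | 124 to 310, 8.0 to 4.9 points | 496 to 310, 3.9 to 4.9 points |
| One cell of 62 | 12 to 31, 30.6 to 17.5 points | 50 to 31, 13.3 to 17.5 points |

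The split in the whole CP meets the plan's standard. A three-way split down to cells of 62 does not.

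**6. Information for the regression.** Expected failures are 0.05 × 620 = 31. The SAP lists 6 demographic, 6 disease or institution, 2 co-infection, 3 liver, 5 other co-morbidity, 1 alcohol, 3 laboratory and 1 prior-treatment variable: 27 in all, or 31/27 ≈ 1.1 failures per candidate. Among experienced patients, at the same rate, 0.05 × 124 ≈ 6 to 0.05 × 310 ≈ 16 failures are expected.

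**The case against.** The strongest defence is that the protocol delegates. It describes the CP groups as those that bear on scheduled regimen and duration, asks the SAP to take the current label into account, and says in Section 7.2 that the label varies by genotype/subtype and liver disease stage. The SAP's definition of the CP rests on the same two characteristics. This is a plausible reason for two factors, but the SAP does not give it. Leave to add detail does not plainly cover removing a named factor, and leave to add covariates does not cover dropping listed ones.

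Small cells are a fair objection to the full three-way split (step 5), but not to an overall split. Interim response tables were repeated by age 70 and by opiate substitution (SAP 4.2.9.3, 4.2.9.4), which the protocol does not name for the CP groups.

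It is also true that prior treatment status is tested against SVR12 in the regression. That yields an exploratory odds ratio, which may not survive elimination at p < 0.05, and not a rate with an interval. The table shells in SAP Part II are not available here; the regression output might print rates by category, but no listed title says so.

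Two stronger readings are tempting. A reader might infer that the omitted factor shifts SVR12 by 12 points. Step 4 shows otherwise: that gap concerns prior null response in cirrhotic G1a patients at 12 weeks, and the comparison arm also mixes genotype 1 subtypes. A reader might also infer that pretreatment status is confined to a regimen table; it is in the regression and the baseline tables too.

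**Conclusion.** The discrepancy stands. Three prior-treatment elements named in the protocol (one group factor and two covariates) are absent from the corresponding parts of the SAP, with no explanation. The consequence is limited: the overall CP rate and its interval do not change, the objective is descriptive, and the documents show naive-versus-experienced gaps of at most about 2.5 points, in non-cirrhotic patients only. For cirrhotic patients they give no such contrast. The 80% against 92% supports restoring the result of prior treatment as a covariate; it does not measure a naive/experienced effect.

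The point is worth correcting because a protocol-specified breakdown of the primary endpoint is missing and the data are already collected (Protocol 9.4.1.1). The precision figures rest on 620 evaluable patients, SVR12 of 95% in both groups and the assumed 20–50% experienced share.

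**What to change.** - Add naive and experienced rows, with Wilson intervals, to the virological response table (tvr) for the CP and CPSFU12: overall, and by cirrhosis status where numbers allow. The plan's own benchmark of 62 patients per cell is a usable guide.
- Restore the latest prior regimen and its result as univariate, descriptive covariates in experienced patients, outside the backward selection.
- If the omission is deliberate, say so in the SAP as a departure from the protocol and give the reason.

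The cost is a few table rows and one small regression output, with no new data. The downside is imprecision: with about 31 failures expected overall and roughly 6 to 16 among experienced patients, results by prior outcome will be descriptive only and should be labelled so.
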